This study examined the relationship between maternal depression and child depression and asthma disease activity mediated by parenting and medication adherence. A sample of 242 children (59% male) with asthma, aged 7 to 17, participated with their mothers. Maternal depression was assessed by the Beck Depression Inventory (BDI), and parenting was observed and rated during family interaction tasks using the Iowa Family Interaction Rating Scale (IFIRS), a widely used valid rating scale. Child depression and anxiety were assessed by the Child Depression Inventory (CDI), the CDRS-R, and the Spielberger State Trait Anxiety Inventory for Children (STAIC). Asthma disease activity was assessed according to NHLBI guidelines, and medication adherence was evaluated with Bender's validated 24-hr recall method (Childhood Asthma Management Program Continuation Study, CAMPCS). Structural equation modeling indicated that maternal depression predicted child depression and anxiety ($B = .39, p < .001$) and, in turn, child depression and anxiety mediated associations between maternal depression, negative parenting and asthma disease activity ($B = .36$,

$p < .001$). Medication adherence did not mediate the link from maternal depression to disease activity.⁵¹

3.3.a.v. Pilot Study 5: Replication of Pilot Study 4 with Fathers and Mothers: Using the same methodology as above, [name] replicated this study with co-habiting fathers and mothers of children with asthma aged 7-17 ($n = 106$, 65% male). Structural Equation modeling showed that the path from maternal depressive symptoms to child depression and anxiety through mothers' parenting behaviors was significant, Chi Square (32, $N 106$) = 57.50, $p < .004$; incremental fit index (IFI) = .89, comparative fit index (CFI) = .87, root mean square error of approximation (RMSEA) = .09; and in turn, child depression and anxiety predicted asthma disease activity ($B = .28$, $p < .05$). Paternal depressive symptoms were linked to child asthma disease activity only through the effect of inter-parent negativity ($B = .32$, $p < .01$) on maternal parenting of the child.⁵²

Significance: These two studies illustrate possible mediating pathways by which caregiver depression impacts the child's asthma by way of depression in the child.

3.3.a.vi. Pilot Study 6: Relationship Between Child Stress and Emotions with Asthma and Airway

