3.3.a.viii. Summary of Findings from Preliminary Studies and the Literature: 1) Our pilot studies show that we can successfully enroll and retain caregivers and children with asthma in research studies. 2) Our pilot data suggest that psychiatric disorders, especially depression, are very common in caregivers of children with asthma. 3) Caregiver depression is associated with more severe childhood asthma and greater service utilization. 4) The literature and [name] and [name]'s preliminary studies suggest that caregiver depression contributes to worse asthma in the child, possibly mediated through stress/depression pathways. 5) The literature suggests that poor adherence is also a likely mediator between caregiver depression and child asthma. 6) Based on our pilot data, treatment of depression in the caregiver was associated with improvement in caregiver depression and a reduction in asthma symptom severity and service utilization by the child.

Given these findings, a study of caregivers and their children with asthma is proposed. **We will test these hypotheses: 1) Improvement in caregiver depression leads to subsequent improvement in the child's asthma control, quality of life, and service utilization. 2) Improved adherence and/or decreased child anxiety/depression mediates the effect of improved caregiver depression on child asthma outcomes.**

To test these hypotheses depressed caregivers will be offered algorithm-based antidepressant treatment by the research psychiatrists, and the impact of changes in caregiver depression on asthma in the child will be examined for 52 weeks (1 year). Mediating pathways linking caregiver depression and the child's asthma will be examined.

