3.4. Statistical Analyses

Aim 1. Determine if improvement in depressive symptoms in caregivers of children with asthma predicts subsequent improvement in the child's asthma control. A CLPM for longitudinal data will be fit using a maximum likelihood SEM in order to explore reciprocal causation between asthma outcomes and depressive symptoms with lagged effect. A separate model will be constructed for each asthma outcome (e.g. CASI, ACT, steroid bursts). The full CLPM with all cross-lagged paths will test if both the asthma outcomes and depressive symptoms predict each other at subsequent visits. For each full model, paths will connect the value of the depressive symptom score (e.g. HRSD) at each visit to the asthma outcome (e.g. CASI) at each subsequent visit (e.g. 4 weeks later, 8 weeks later). Another set of paths will connect the asthma outcome at each visit to the HRSD at each subsequent visit. The full model will be compared to reduced models containing either the first set of paths or the second set. We hypothesize that the model with the first set of paths will provide a better fit than the second set. The models will be compared on goodness of fit criteria, a non-significant X^2 p-value .05 or more, fit indices .90 or more, RMSEA .05 or less, and significant path coefficients.⁶⁸⁻⁷⁵ Extensive overviews of the use of this CLPM for longitudinal data analyses are given by Cole and Maxwell and MacKinnon.^{70, 75} We will follow Cole and Maxwell's⁷⁰ guidelines for testing the proposed causal relationship, caregivers' depressive symptoms preceding child's asthma outcomes, with longitudinal data using SEM software *Mplus*. We will control for variables that might impact depressive symptoms or asthma response including age, gender and race/ethnicity. The primary analysis for this aim will use CASI scores for the child and caregiver HRSD scores. The HRSD is a widely used clinician-rated depression scale while the CASI scores take into account both asthma symptoms and asthma medication use to treat symptoms. Similar analysis will be conducted using the QIDS-SR as the depression measure and STAI as a caregiver anxiety measure. ACT scores and steroid bursts will be used as well as CASI scores in the analysis.

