
Aim 3. Determine if improvement in depressive symptoms in the caregivers of children with asthma predicts improvement in asthma-related QOL in the caregiver and child. We will use the same approach outlined above under Aim 1 above but substituting the quality of life measure (PAQOL and PACQOL) in place of the asthma control measure.

Aim 4. Examine medication adherence and child anxiety/depression as possible mediators transmitting the effect of decreased caregiver depression on asthma control and unscheduled service utilization. The goal of Aim 4 is to validate the following relationships:

Caregiver HRSD (1) → medication adherence or child anxiety/depression (2) → child asthma outcomes (3)

The relationship between (1) and (3) is considered in Aim 1. For Aim 4, two sets of CLPM analyses, (1) → (2) and (2) → (3), will be done independently as described for Aim 1. The first set of analyses will determine if caregiver HRSD improvement (1) precedes child adherence (CAMPCS scores) and anxiety/depression

improvement (SCARED, CDI-Full Length scores) (2). Separate models will be fit for adherence and anxiety/depression. The second set of analyses will determine if child adherence and anxiety/depression improvement (2) precedes child asthma outcome improvement (3). Separate models will be fit relating adherence to each asthma outcome and relating anxiety/depression to each asthma outcome (6 models altogether). Similar analysis will be conducted replacing the HRSD with the caregiver scores on the QIDS-SR and STAI.

Missing Data: The analyses described here for the Primary Aim and Secondary Aim 2 will make use of data from all available subjects, even subjects with some missing data. Also, these models are unbiased if the missing data are missing at random (MAR).⁷⁶ However, in case the MAR assumption is not satisfied, we will investigate the effect of dropouts on the final results by introducing a variable into the models to indicate whether the patient dropped out or completed.⁷¹ If this dropout status variable is significant, then sensitivity analyses will be done to determine the possible effects of dropouts on the final results.^{72-74, 76, 77} The impact of missing data in the structural equation models will be assessed by using full information maximum likelihood.⁷⁸

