Power: No data exist on which to base a power analysis. However, the hypothesis tests used here involve testing regression coefficients. To obtain an approximate idea of the power of our tests, we can refer to the test of a regression coefficient that can be detected with 80% power given a sample of 175. If we conservatively assume 10 predictors for the Primary Aim and Secondary Aim 2, then an effect size of $f^2 = 0.10$ could be detected. This effect size is classified as small ($f^2 = 0.02$) to medium ($f^2 = 0.15$) according to Cohen.⁶⁹ In the full model for Secondary Aims 1, 2 and 3 there are 13 measurement occasions and approximately 200 paths; however, the hypotheses to be tested involve the 78 paths between each visit and each later visit. Given this number of predictors to be tested, an effect size of 0.31 could be detected with 80% power. This effect size is classified as medium ($f^2 = 0.15$) to large ($f^2 = 0.35$) according to Cohen.⁶⁹

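### Aim 4 never puts caregiver depression, the mediator and asthma in one model, so it cannot separate mediation from a parallel effect of caregiver depression

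*Combined protocol and SAP*

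**What the plan says.** Hypothesis 2 (section 3.3.a.viii) is that "Improved adherence and/or decreased child anxiety/depression mediates the effect of improved caregiver depression on child asthma outcomes". Section 3.2 promises to study the two routes together and compare what each adds, and section 3.3.b says in general terms that SEM will test mediation.

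The operative text is Aim 4 in section 3.4. It splits the chain into HRSD to mediator and mediator to asthma; these "will be done independently as described for Aim 1". The HRSD-to-asthma link is left to Aim 1, whose model contains no mediator. On the first step: "Separate models will be fit for adherence and anxiety/depression". On the second: "The second set of analyses will determine if child adherence and anxiety/depression improvement (2) precedes child asthma outcome improvement (3"). That step has six models, which fits 2 mediators × 3 asthma outcomes, one mediator in each.

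The covariates come from Aim 1: "We will control for variables that might impact depressive symptoms or asthma response including age, gender and race/ethnicity". Caregiver HRSD is not among those named. Nowhere does the plan define an indirect effect, a direct effect, an interval for either, or a rule for combining the two steps.

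**The concern.** Hypothesis 1 says caregiver depression drives asthma. The first step of Aim 4 says it drives the mediator. If both are true, HRSD is a common cause of the two variables in the second step. Leaving it out biases the mediator-to-asthma path in the direction the investigators expect. Two significant steps are what mediation would produce, but also what a purely parallel effect would produce.

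An adherence or child-anxiety route could thus be declared validated when caregiver depression reaches asthma by another path. The direct effect, the mediated share and the comparison of the two routes would stay unknown. Section 3.1.c says the findings are to support a later trial aimed at these mediators. Aims 1 to 3 are not affected.

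**Working it through.** **1. The plan's own power figures.** Section 3.4 gives N=175, 80% power, f²=0.10 for 10 predictors, and for the cross-lagged models "the hypotheses to be tested involve the 78 paths between each visit and each later visit" (13×12/2 = 78): "Given this number of predictors to be tested, an effect size of 0.31 could be detected with 80% power". The check uses a noncentral F test of all k coefficients, with denominator df 175−k−1, noncentrality f²×175 and α=0.05 (assumed; none is stated).
- k=10: df 10 and 164, noncentrality 17.5, power 81.0%.
- k=78: df 78 and 96, noncentrality 54.25, power 80.2%.

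Both figures reproduce. Neither concerns an indirect effect.

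**2. Bias in the second step.** The plan states that no data exist for a power analysis, so the path values below are assumptions. Let X be HRSD, M the mediator and Y asthma, each with autoregression r and independent unit-variance innovations. X acts on M and on Y with the same lag-1 effect a, and M has no effect on Y. In the stationary state:
- v = Var(X) = 1/(1−r²)
- s = Cov(X,M) = Cov(X,Y) = r·a·v/(1−r²)
- q = Cov(M,Y) = (a²v + 2ras)/(1−r²)
- w = Var(M) = Var(Y) = v + q

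Regressing Y on its own last value and the last M, without X, gives M the coefficient a·s/(w+q). It is already standardised because M and Y have equal variance.

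Example, r=0.5 and a=0.2: v=1.333; s=0.5×0.2×1.333/0.75=0.178; q=(0.0533+0.0356)/0.75=0.119; w=1.452. The spurious path is 0.2×0.178/(1.452+0.119)=0.023, against a true value of 0.

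| a | r=0.5 | r=0.7 |
|---|---|---|
| 0.1 | 0.006 | 0.012 |
| 0.2 | 0.023 | 0.038 |
| 0.3 | 0.043 | 0.061 |

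Once prior X is in the model the coefficient is zero.

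**3. Effects matching the plan's f².** Treat f² as the partial effect of X's history on Y given Y's history. Then a = √[f²(1 − r²/(1+f²))]. For f²=0.10 this gives 0.28 (r=0.5) and 0.24 (r=0.7); for f²=0.31, 0.50 and 0.44.

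**4. How often both planned steps are significant with no mediation.** N=175, 13 occasions, 600 replicates per setting; entries are for r=0.5 / r=0.7. The joint test covers all 78 paths, with a small-sample-corrected likelihood ratio and adjustment for all earlier own values. The lag-1 test uses one pooled coefficient with person-clustered standard errors; it is not the structure the plan describes.

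| HRSD effect | 78-path test | Pooled lag-1 |
|---|---|---|
| a=0.1 | 3% / 5% | 6% / 14% |
| a=0.2 | 5% / 13% | 26% / 72% |
| a=0.3 | 12% / 45% | 63% / 99% |
| f²=0.10 | 7% / 18% | 50% / 90% |
| f²=0.31 | 40% / 86% | 98% / 100% |

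With prior HRSD in the second step, the range is 3% to 9% throughout.

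Aim 1 also compares the forward with the reverse direction. Requiring the forward statistic to be larger gives, for the 78-path test, 7%/17% at f²=0.10 and 33%/50% at f²=0.31; for lag-1, 35%/49% and 51%/49%. In this scenario M and Y are interchangeable, so the directional rule comes close to a coin toss.

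**5. Different assumptions.** With autoregression 0.6 for HRSD and 0.5 for the others, 14 visits, pooled lag-1 paths and 1,000 runs, both steps pass in 8.6%/46.6%/92.2% for a=0.1/0.2/0.3. Adding lagged HRSD gives 3.6%/3.3%/2.9%, near the nominal 2.5% upper tail. With real mediation (both paths 0.2, no direct effect), both versions pass in 100% of runs.

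**The case against.** - **The omission is partly read from silence.** The Aim 1 covariate list is open-ended, the plan cites longitudinal-mediation literature, and section 3.3.b says SEM will test mediation. That is fair as to intent. But only demographics are named, the guidelines are invoked for depression preceding asthma, and a time-varying HRSD series would make this a three-variable model, not the two-variable one described.
- **The largest percentages come from pooled lag-1 tests.** This stands: they show what happens if paths are pooled, not what the written 78-path test would do. Under that test, weak effects give little or no inflation, and the f² values are detectable sizes, not expected ones.
- **The 78-path figures depend on the model.** One variant with only lag-1 own paths gave 23%/75% at f²=0.31, and 20%/60% after adding the plan's chi-square criterion. A further simulation gave about 40%/86% and found that the inflation held with lag-1 own paths, so the lower values were not confirmed. It gave about 12%/20% at f²=0.10. The plan's absolute fit criteria are not in the table above.
- **The pilot evidence is limited.** Pilot Study 4 reports: "Medication adherence did not mediate the link from maternal depression to disease activity". It does not say which link failed, and separate models could reveal a link that is absent. It shows that non-mediation by adherence is realistic, not that the parallel pattern occurred.
- **Mediation is not the primary aim.** True, but it is one of the two stated hypotheses.

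**Conclusion.** The concern holds. As written, no Aim 4 model contains HRSD, a mediator and asthma together, and no indirect or direct effect is specified. The analysis therefore cannot distinguish Hypothesis 2 from a parallel effect, nor compare the two mediators as section 3.2 promises. That conclusion follows from the structure and needs no simulation.

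The size of the false-mediation risk does rest on assumptions: equal HRSD effects on mediator and asthma, no true mediator effect, and autoregression of 0.5 or 0.7. Under the 78-path test the risk is negligible for weak effects (3% to 5% at a=0.1) and large for strong ones (40%/86% at f²=0.31). It is larger still if paths are pooled across visits. Including HRSD brings it back to 3% to 9%. Unmeasured common causes would remain in any case, but this one is measured and is part of the hypothesis.

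**What to change.** Replace the independent Aim 4 models with one cross-lagged model per asthma outcome that contains HRSD, adherence, child anxiety/depression and the outcome. Keep each variable's own lags; the chain from HRSD at one visit to the mediators at the next and asthma at the one after; and the direct HRSD-to-asthma path. Hold paths equal across visits for stability. Pre-specify each lagged indirect effect with a bootstrap confidence interval, and report the direct effect and both mediators' contributions. At a minimum, add prior HRSD to every mediator-to-asthma model.

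The cost is SAP wording and Mplus code; Table 2 schedules all the measures at every visit. The price is power. With an assumed true mediator effect of 0.05 and HRSD effect of 0.2 (300 replicates, autoregression 0.5/0.7), adding HRSD leaves 79%/92% power with paths held equal, but only 10%/19% with 78 free paths. The planned models show 98%/100% and 27%/70%, part of which is confounding. The minimum change is therefore weak unless the equality constraints are adopted too, which departs from the Aim 1 structure. Power and estimability of the full model with bootstrapped indirect effects were not calculated and should be checked by simulation before the SAP is finalised.

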Buffalo: The Buffalo pediatric asthma service ([name], co-I) that will be used for enrollment is a three-site practice with a diverse patient demographic. The main clinic site is an inner-city clinic attached to the Women and Children's Hospital of Buffalo. In addition, there is a suburban satellite clinic and a suburban/rural satellite clinic. The Buffalo pediatric asthma service has 1160 patients in the age range proposed for the study and 315 new patients in this age range each year. Given these numbers, if 26% of caregivers have current MDD (as in our pilot study), then over a 4 year enrollment period the site will have 547 eligible participants. To enroll 98 participants, 18% of these will need to agree to participate.

Participant retention: We will use established methods for recruiting and retaining populations over long periods of time. Drs. [name] and [name] have used these methods throughout their multi-visit studies and obtained excellent retention statistics (95% completion of a 6 week study). [name] (PI) was an investigator on TMAP, a large multisite study using treatment algorithms for one year in patients with psychiatric illnesses in a similar fashion as the proposed study. In the MDD module of TMAP, retention was 100% at 3 months, 99.5% at 6 months, 83.2% at 9 months and 75.9% at 12 months. To maximize retention in the proposed study, multiple contact numbers (home, cell, work, family, friends), mailing addresses, and e-mail addresses will be obtained. Participants will be compensated appropriately for participation, transportation, time, and effort. Participants will have contact with research staff every 2-4 weeks either by phone or in person to keep them engaged in treatment. Participants are in the study for 52 weeks even if they miss some appointments, and we will collect as much data from each participant as possible. It is noteworthy that our data analytic procedures have robust methods of dealing with missing data. In addition, we propose enrolling 196 participants, rather than the 175 needed based on a power analysis, to allow for some early attrition.

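### Dropout sensitivity analyses depend on a significant dropout indicator that does not test MAR, and FIML cannot fill the gap, so a departure from MAR can go unexamined

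*Combined protocol and SAP*

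**What the plan says.** Section 3.4, Missing Data, states that the planned models are unbiased under MAR. In case MAR fails, the plan will look at dropout by "introducing a variable into the models to indicate whether the patient dropped out or completed". That step carries no condition. The next one does: "If this dropout status variable is significant, then sensitivity analyses will be done". No significance level is given for the indicator. The sensitivity analyses are identified only by citation, without a named model, adjustment or range.

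The paragraph ends: "The impact of missing data in the structural equation models will be assessed by using full information maximum likelihood". Aims 1, 3 and 4 are cross-lagged panel models (CLPMs) fitted by SEM, so this sentence covers the primary analysis of Aim 1: "The primary analysis for this aim will use CASI scores for the child and caregiver HRSD scores". Aim 2 is a Poisson mixed model of event rates with each caregiver's HRSD slope as predictor.

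On expected loss, section 3.3.c.ii reports that retention in the depression module of the Texas Medication Algorithm Project (TMAP) was "75.9% at 12 months". It then gives this trial's own allowance: "we propose enrolling 196 participants, rather than the 175 needed based on a power analysis, to allow for some early attrition".

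No non-MAR analysis that runs unconditionally appears anywhere else in the document.

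**The concern.** The plan uses a significance test to decide whether MAR needs to be questioned. The test cannot answer that question. MAR is a statement about values that were not observed, given those that were. A dropout indicator contrasts the observed data of those who left with the observed data of those who stayed. If dropout depends on recorded scores, the indicator can be significant although MAR holds. If dropout depends on where a family's trajectory was heading, the indicator can be silent although MAR fails. A non-significant result may also only reflect the small number of dropouts.

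FIML does not repair this in the SEMs. It uses all available data and is valid under MAR, which makes it a reasonable primary estimator, but its output carries no information about departure from MAR.

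The trial has no randomised comparator (section 3.3.b), so its conclusions rest on within-family change. Dropout related to unobserved change bears directly on that. Under the plan as written, the primary conclusion could be reported under MAR alone, with a non-significant indicator taken as reassurance.

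**Working it through.** **Inputs.** From the documents: 196 enrolled and 175 needed; TMAP 12-month retention 75.9%; baseline plus 13 assessments. Assumed, because the documents give none: a two-sided 5% level for the indicator, standardised differences of 0.2 to 0.5 SD between dropouts and completers, and the variance components in step 3.

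**1. The plan's own figures.** The Power paragraph gives detectable effects at 80% power and N = 175. I used a noncentral F test with noncentrality f² × N, numerator df equal to the number of predictors, denominator df = N − predictors − 1, and a 5% level. Power is 81.0% at f² = 0.10 with 10 predictors and 80.2% at f² = 0.31 with 78. Both figures reproduce, so 5% appears to be the plan's working level, which supports assuming it for the indicator.

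The attrition allowance is 1 − 175/196 = 10.7%, or 21 of 196. TMAP's loss is 1 − 0.759 = 24.1%, and 196 × 0.241 = 47.

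**2. Chance that the condition is met, as a two-group comparison.** With n_c completers and n_d dropouts, SE = √(1/n_c + 1/n_d) in SD units, and power ≈ Φ(SMD/SE − 1.96).

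- 24.1% dropout: SE = √(1/149 + 1/47) = 0.167. At 0.3 SD: 0.3/0.1673 = 1.79, and Φ(1.79 − 1.96) = 43%.
- 10.7% dropout: SE = √(1/175 + 1/21) = 0.231. At 0.3 SD: 0.3/0.2309 = 1.30, and Φ(1.30 − 1.96) = 25%.

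Noncentral t results:

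| Difference | 24.1% dropout (149 v 47) | 10.7% dropout (175 v 21) |
|---|---|---|
| 0.2 SD | 22.1% | 13.8% |
| 0.3 SD | 43.0% | 25.3% |
| 0.4 SD | 66.2% | 40.7% |
| 0.5 SD | 84.5% | 57.7% |

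The normal approximation agrees to within half a percentage point (66.7% and 84.8% in the last two rows of the first column). The chance passes 50% at 1.96 × SE: 0.33 SD with 24.1% dropout and 0.45 SD with 10.7%.

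**3. Does the indicator separate MAR from non-MAR?** This was checked by simulating one repeated outcome in 196 dyads over 14 visits. Assumed values: random-intercept SD 0.7, random-slope SD 0.5, residual SD 0.55, true mean slope −0.5. The fit was generalised least squares with known variances. The indicator was a main effect at the 5% level. There were 400 runs per setting at 10.7% dropout and 200 at 24.1%.

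| What drives dropout (log-odds per SD) | Dropout | Indicator significant | Bias in mean slope |
|---|---|---|---|
| Last observed value, MAR (0.5) | 10.7% | 46% | 0.000 |
| Last observed value, MAR (0.5) | 24.1% | 78% | +0.006 |
| Current unseen value, non-MAR (0.25 / 0.5 / 1.0) | 10.7% | 14% / 39% / 88% | 0.000 / −0.001 / −0.013 |
| Current unseen value, non-MAR (0.25 / 0.5 / 1.0) | 24.1% | 26% / 66% / 99% | −0.008 / −0.017 / −0.030 |
| Individual slope, non-MAR (0.25 / 0.5 / 1.0) | 24.1% | 5% / 5% / 9% | −0.022 / −0.042 / −0.085 |

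The condition is often met where MAR holds and bias is negligible. It is met at little more than the false-positive rate in the setting with the largest bias: 0.085/0.5 = 17% of the true slope at the strongest dependence. In those slope-driven settings an indicator-by-time term was significant in 11%, 18% and 56% of runs. That is better, but still not a basis for deciding whether to look further.

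**The case against.** Several stronger readings are tempting, and the documents do not support them.

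- *A departure from MAR will usually be missed.* At 24.1% dropout the condition is met more often than not above about 0.33 SD, and in 99% of runs under one strong non-MAR mechanism. Across the simulated non-MAR settings the chance runs from about 5% to 99%.
- *The primary aim has no unconditional check.* The indicator is introduced before any condition applies, and it is a limited look at dropout. Whether it enters the CLPMs is unclear: the Missing Data paragraph speaks of a Primary Aim and a Secondary Aim 2, while section 3.4 numbers Aims 1 to 4. That is an ambiguity, not an established absence.
- *A quarter of families are expected to leave.* The 75.9% is TMAP's result, not a forecast for this trial. The plan's own allowance is 10.7%. The lower rate weakens the indicator further, so this does not rescue the condition.
- *Dropout linked to depression breaks MAR.* HRSD is recorded at baseline and every four weeks. Dropout that depends on recorded HRSD is MAR, and FIML handles it when those scores are in the model. The documents say nothing about why families would leave.
- *The indicator is only a main effect.* The text does not say so. The sources cited for the indicator and the sensitivity analyses include titles on pattern-mixture models and on modelling dropout, and the source cited for FIML has a title about data not missing at random. Titles do not specify an analysis, so the fair criticism is under-specification.

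The calculations are also simpler than the planned models: a two-group contrast and a single-outcome trajectory, not a 13-occasion CLPM or a Poisson mixed model. They illustrate the behaviour of the condition; they do not estimate its power in this trial or the bias in a cross-lagged path.

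None of this answers the central point. The follow-on analyses are conditional on a test that does not address MAR, and the SEM sentence offers a MAR method as the assessment.

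**Conclusion.** The concern holds in a limited form. A real departure from MAR can go unexamined, including for the primary HRSD-CASI model, because the sensitivity analyses wait on an indicator that is not a test of MAR and FIML cannot reveal such a departure. This part follows from the text and the definition of MAR and needs no numerical assumption.

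The size is illustrative. For differences of 0.2 to 0.5 SD the condition would be met about 22% to 85% of the time at TMAP's dropout and 14% to 58% at the plan's own allowance. These figures rest on the assumed level, the assumed differences and the two-group simplification. They do not show that a departure would usually be missed, and nothing in the documents shows that dropout in this trial will be non-MAR. The point should be corrected before analysis.

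**What to change.** In section 3.4, Missing Data:

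1. State that FIML/ML under MAR is the primary estimator, and that it is not an assessment of departure from MAR.
2. Delete the requirement that the indicator be significant. The indicator may stay as a description of dropout.
3. Pre-specify a non-MAR sensitivity analysis, pattern-mixture or delta-adjusted, in line with the methods already cited. Run it whatever the indicator shows, for the primary Aim 1 HRSD-CASI model and the Aim 2 HRSD/ER model. Give the adjustment and its range in advance.
4. Let the HRSD effect, and change over time where applicable, differ by dropout status.
5. Name the models by the Aim 1 to 4 numbering, and say whether the indicator enters the CLPMs.

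For Aim 2, define the missingness separately for HRSD and for events: section 3.3.d.iv supplements caregiver reports of utilisation from medical and pharmacy records, so the two may be missing for different families.

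The cost is SAP wording and modest extra analysis, with no new data and no burden on families. It is somewhat more for the CLPM, where the plan counts 78 lagged paths and the adjustment has to be defined across visits.
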